1. PROTOCOL SUMMARY

1.1. Synopsis

Protocol Title: A randomized, double blind, parallel group study of the efficacy and safety of Mepolizumab as adjunctive therapy in patients with severe asthma with eosinophilic inflammation

Rationale:

This study proposed to be conducted in China is similar in design to the global pivotal study MEA115588 which has established favourable benefit risk profile of mepolizumab in severe asthmatics with eosinophilic inflammation. While patients with severe asthma represent only a small percentage (5-10%) of the asthmatic population, they incur the greatest direct costs for the treatment of asthma. Current asthma treatment guidelines offer minimal options for the severe asthmatic patient on intensive therapy with frequent exacerbations. There is a significant unmet medical need to provide better treatment options for this segment of the asthma population. Previous studies in severe asthmatic patients with eosinophilic inflammation have demonstrated a reduction in the frequency of clinically significant exacerbations and a reduction in oral corticosteroids (OCS) in OCS-dependent subjects with mepolizumab which has also exhibited a favorable safety profile. This study is a Phase III study in Chinese population, to evaluate the efficacy and safety of mepolizumab in severe asthmatics with eosinophilic airway inflammation.

Objectives and Endpoints:

Objectives	Endpoints
Primary Efficacy	
Frequency of clinically significant exacerbations of asthma over the 52-week treatment period.
 
Clinically significant exacerbations are defined as: Worsening of asthma which requires use of systemic corticosteroids (SCS)¹ and/or hospitalizations and/or Emergency Department (ED) visits.
 
¹For all subjects, i.v. or oral corticosteroid for at least 3 days or a single IM Corticosteroid (CS) dose is required. For subjects on maintenance systemic corticosteroids (SCS), at least double the existing maintenance dose for at least 3 days is required.

Secondary Efficacy	
 To evaluate the effects of mepolizumab compared with placebo on a range of clinical markers of asthma control, 
 Time to first clinically significant exacerbations Mean change in St. George's Respiratory Questionnaire (SGRQ) at Week 52

Objectives	Endpoints

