5.1. Inclusion Criteria

A subject will be eligible for inclusion in this study only if all of the following criteria apply:

1. **Informed Consent:** Able to give written informed consent prior to participation in the study, which will include the ability to comply with the requirements and restrictions listed in the consent form. Subjects must be able to read, comprehend, and write at a level sufficient to complete study related materials.
2. **Age and Weight:** At least 12 years of age at Visit 0 and a minimum weight of 40 kg.
3. **FEV1:** Persistent airflow obstruction as indicated by:
 - For subjects ≥ 18 years of age at visit 1, a pre-bronchodilator FEV₁ $< 80\%$ predicted normal values calculated by Quanjer reference equations [[Quanjer, 2012](#)]
 - For subjects 12-17 years of age at visit 1:
 - A pre-bronchodilator FEV₁ $< 90\%$ predicted ([Quanjer, 2012](#)) recorded at Visit 1 OR
 - FEV₁: FVC ratio < 0.8 recorded at visit 1
4. **Eosinophilic information:** Prior documentation of eosinophilic asthma or high likelihood of eosinophilic asthma as per Randomization Criteria 1.
5. **Inhaled Corticosteroid:** Regular treatment with high dose inhaled corticosteroid (ICS) in the 12 months prior to Visit 1, of which at least 9 months accumulated documented is required, the 3 months prior to Visit 1 is mandatory. With or without maintenance oral corticosteroids(OCS)*.
ICS dose must be ≥ 500 mcg/day fluticasone propionate (FP) or equivalent daily (for ICS/LABA combination preparations, Seretide 50/250 mcg bid and above or equivalent will meet this ICS criteria). *[Maintenance OCS is defined as a prescribed regimen of a minimum average daily dose of prednisone 5mg (or equivalent)].
6. **Controller Medication:** Current treatment with one or more additional controller medication, besides ICS. At least one additional controller medication must have

been regularly used for at least 3 months prior to Visit 1. [e.g., long-acting beta-2-agonist (LABA), leukotriene receptor antagonist (LTRA), or theophylline]

7. **Exacerbation history:** Previously confirmed history of two or more exacerbations requiring treatment with systemic CS (intramuscular (IM), intravenous, or oral), in the 12 months prior to Visit 1, despite the use of high-dose ICS. For subjects receiving maintenance CS, the CS treatment for the exacerbations must have been a two-fold increase or greater in the dose for at least 3 days is required.

8. **Gender:** Male or Female

Female participants:

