1.1. Objectives, Estimands and Endpoints

Objectives	Endpoints
Primary	
 To evaluate the efficacy of mepolizumab 100 mg subcutaneous (SC) every 4 weeks versus placebo on the frequency of clinically significant exacerbations in adult and adolescent Chinese subjects with severe asthma with eosinophilic airway inflammation. 
Frequency of clinically significant exacerbations of asthma over the 52-week treatment period. Clinically significant exacerbations are defined as: Worsening of asthma which requires use of systemic corticosteroids and/or hospitalizations and/or Emergency Department (ED) visits.
 
For all subjects, oral corticosteroid for at least 3 days or a single IM Corticosteroid (CS) dose is required. For subjects on maintenance systemic corticosteroids, at least double the existing maintenance dose for at least 3 days is required.

Secondary	
 To evaluate the effects of mepolizumab compared with placebo on a range of clinical markers of asthma control, including exacerbations, lung function, and quality of life. 
 Time to first clinically significant exacerbations Mean change in St. George's Respiratory Questionnaire (SGRQ) at Week 52 Frequency of exacerbations requiring hospitalisation (including intubation and admittance to an ICU) or ED visits over the 52-week treatment period Frequency of exacerbations requiring hospitalisation over the 52-week treatment period Mean change from baseline in clinic pre-bronchodilator FEV1 at Week 52
Safety	
 To evaluate the safety and tolerability of mepolizumab compared with placebo, in subjects with severe asthma with 
 Adverse Event including systemic (i.e. allergic [type I hypersensitivity] and Other systemic) and injection site reactions reported throughout the 52-week treatment period Haematological and clinical chemistry parameters

Objectives	Endpoints
eosinophilic inflammation	
 • Vital signs (pulse rate and systolic and diastolic blood pressure) • 12-lead ECG • Frequency of subjects with anti-mepolizumab antibody positive results
Others	

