4.1.3. Definition of endpoint(s)/estimands

The primary endpoint is the frequency of clinically significant exacerbations (the same as protocol defined exacerbations) of asthma over the 52 weeks treatment period expressed as an exacerbation rate p.a.

Exacerbation from the start of treatment until 4 weeks after the last dose of study drug will be used in the analysis. Exacerbations which are separated by less than 7 days will be treated as a continuation of the same exacerbation.

The estimand is described by the following attributes:

- Population: Chinese participants with severe eosinophilic asthma.
- Treatment condition: mepolizumab 100mg SC given every 4 weeks compared to placebo every 4 weeks, both treatments given on top of standard of care. Further details on standard of care can be found in Section 6 of Protocol.
- Variable: number of clinically significant exacerbations over 52 weeks.
- Summary measure: annualised rate of exacerbations. Comparison between the mepolizumab arm and placebo will be assessed with the rate ratio.
- Intercurrent events:
 - Study treatment discontinuation-hypothetical strategy
- Rationale for estimand:

Interest lies in the treatment effect when medication is taken as directed. For participants discontinuing randomised medication, use of a hypothetical strategy addresses treatment effects attributable to mepolizumab in the hypothetical scenario where participants would not discontinue from treatment.

Since this is a bridging study, the results from MEA115588 will be borrowed and compared with the data from this study. To ensure comparability between two studies, the Estimand framework including analysis models will be similar with MEA115588.

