
 Mean change from baseline in daily salbutamol/albuterol use Mean change from baseline in daily asthma symptom scores Mean change from baseline in awakening at night due to asthma symptoms requiring rescue medication use Mean change from baseline in morning PEF
Missing data imputation
No imputation will be done for missing data.
Model Specification, Checking & Diagnostics, Results, Presentation

 These endpoints will be summarized by descriptive statistics: mean, SD, median, min and max. The daily data (excluding days with missing data) will be aggregated over 4-week periods (weeks 1-4, 5-8, ..., 48-52). Data for each 4-week period, and change from baseline for each 4-week periods will be summarized by treatment group.

Endpoint(s)

 Mean number of days with oral corticosteroids taken for clinically significant exacerbations Total prednisone (or equivalent) exposure for clinically significant exacerbations over the 52-week treatment period
Missing data imputation
Only the observed data before discontinuation of study treatment will be used and no imputation will be done for missing data.
Model Specification, Checking & Diagnostics, Results, Presentation

 Total number of days of oral corticosteroids use for clinically significant exacerbations per subject will be summarised by treatment arm

Endpoint(s)

 Total prednisone equivalent dose per clinically significant exacerbation per subject will be summarised by treatment arm. A summary table for OCS only and OCS plus other systemic routes of administration (oral, IV and IM) corticosteroids will be produced

Endpoint(s)

 Frequency of all exacerbations
Missing data imputation
The method for missing data imputation will be the same as the primary efficacy analysis (see Section 4.2.1 for details).
Model Specification, Checking & Diagnostics, Results, Presentation

 These endpoints will be analyzed using the same methodology as the primary analysis in Section 4.2.1

Endpoint(s)

 Time to first exacerbation Time to withdrawal from study treatment due to asthma exacerbations Time to first exacerbation requiring hospitalization or ED visit
Model Specification, Checking & Diagnostics, Results, Presentation

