6.2.10. Evaluation Process of Clinically Significant Asthma Exacerbations

In order to provide an objective assessment of the circumstances linked to the clinical decision that defines asthma exacerbations, the investigator must take into account changes on one or more of the following parameters recorded in the subject's eDiary:

- decrease in morning peak flow
- increase in the use of rescue medication
- increase in the frequency of nocturnal awakening due to asthma symptoms requiring rescue medication use
- increase in overall asthma symptom score

This clinical verification process is designed to validate that the exacerbations recorded by the investigator are associated with objective evidence, such as the eDiary parameters described above.

The following steps will be followed for verification of asthma exacerbations:

1. Clinical Review will be performed to evaluate each exacerbation to determine the event meets the protocol definition. Follow up will be done with the Primary Investigator in the event that data needs to be queried.
2. The medical monitor will review each exacerbation in InForm and verify the exacerbation against eDiary data (extracted from the PHT Portal), to confirm the exacerbation was associated with one of the following:
 - a. Decreases in peak flow:
 - i. as flagged by an alert in the eDiary (Decrease in morning PEF $\geq 30\%$ on at least two of three successive days, compared with baseline (last 7 days of run-in)) or;
 - ii. any other decrease judged by the medical monitor to be clinically significant
 - b. Increase in rescue medication use:
 - i. as flagged by an alert in the eDiary (An increase of $\geq 50\%$ in rescue medication on at least two of three successive days, compared with the average use for the previous week) or;
 - ii. any other increase judged by the medical monitor to be clinically significant (e.g. ≥ 4 puffs in 2 or more consecutive days)
 - c. Increase in nocturnal awakenings due to asthma symptoms requiring use of rescue
 - i. as flagged by an alert in the eDiary (Awakening due to asthma symptoms requiring successive nights) or;
 - ii. any other increase judged by the medical monitor to be clinically significant
 - d. Changes in Asthma Symptoms (increase in overall asthma symptom score):
 - i. as flagged by an alert in the eDiary (A symptom score of 5 for at least two of three successive days) or;

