6.2.13. Reasons for Exclusion from the Per Protocol Analysis

Subjects with protocol deviations considered to potentially have an effect on efficacy will be removed from the Per Protocol (PP) population. Determination of the Per Protocol population will be done blinded to treatment before the database is frozen. The reason for exclusion for any subject will be documented.

Reasons for exclusion from the PP population may be included:

- No persistent airflow obstruction as indicated by pre-bronchodilator FEV1 <80% predicted (NHANES III) for subjects ≥ 18 years of age recorded at Visit 1 (predicted pre-bronchodilator FEV1 <90% or FEV1/FVC <0.8 for subjects 12 to 17 years of age) (see Inclusion Criterion 3)
- Absence of regular treatment with high dose ICS (ICS dose must be ≥ 500 mcg/day fluticasone propionate (FP) or equivalent daily (for ICS/LABA combination preparations, Seretide 50/250 mcg bid and above or equivalent will meet this ICS criteria.) in the 12 months prior to Visit 1, of which at least 9 months accumulated documented is required (see Inclusion Criterion 5)
- Absence of current treatment with one or more additional controller medication, besides ICS, and at least one additional controller medication must have been regularly used for at least 3 months prior to Visit 1. (see Inclusion Criterion 6)
- No eosinophilic airway inflammation (see Randomization Criterion 1) as defined by:
 - Peripheral blood eosinophil level of ≥ 300 cells/ μ L documented in the 12 months prior to visit 1 that is related to asthma OR
 - Peripheral blood eosinophil level of ≥ 150 cells/ μ L demonstrated at Visit 1 that is related to asthma
- <2 asthma exacerbations in the 12 months prior to Visit 1 (see Inclusion Criterion 7)
- No evidence of asthma (see Randomization Criterion 2) as documented by either:
 - Airway reversibility (FEV1 $\geq 12\%$ and 200ml) demonstrated at Visit 1 or Visit 2 OR
 - Airway reversibility (FEV1 $\geq 12\%$ and 200ml) documented in the 12 months prior to visit 2 (randomization visit) OR
 - Airway hyperresponsiveness (PC₂₀ of <8 mg/mL or PD₂₀ of <7.8 μ mol methacholine/histamine or positive mannitol test) documented in the 12 months prior to visit 2 (randomization visit) OR
 - Airflow variability in clinic FEV1 $\geq 20\%$ between two clinic visits documented in the 12 months prior to visit 2 (randomization visit) (FEV1 recorded during an exacerbation will not be valid) OR

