6.2.14. Daily Corticosteroid Dose Administered for an Exacerbation

Only corticosteroids administered via oral, IV and IM routes are to be considered when calculating a subject's daily prednisone/prednisolone dose associated with an exacerbation. All steroids administered via a sublingual route will also be considered as oral.

The below corticosteroid conversion factors will be used, regardless of the route of administration, to scale each corticosteroid dose to a prednisone equivalent dose. These three routes of administration (oral, IV and IM) are to be considered equivalent as it has been noted that the bioavailability of methylprednisolone is considered to be roughly equivalent following administration as an oral, IV or IM steroid [[Kenalog-40 prescribing information](#), 2011; [Antal, 1983](#)]. If there are seen to be two corticosteroid records associated with an exacerbation that are seen to overlap on a particular study day, these overlapping records will be summed in order to obtain a total prednisone/prednisolone equivalent dose for the day in question.

Standardized Medication Name	Scaling Factor
Betamethasone	8.33
Betamethasone Dipropionate	8.33
Betamethasone Sodium Phosphate	8.33
Cortisone	0.2
Cortisone Acetate	0.2
Cortivazol	17
Deflazacort	0.833
Dexamethasone	6.67
Dexamethasone Sodium Phosphate	6.67
Dexamethasone Acetate	6.67
Fludrocortisone Acetate	0
Hydrocortisone	0.25
Hydrocortisone Sodium Succinate	0.25
Hydrocortisone Sodium Phosphate	0.25
Meprednisone	1
Methylprednisolone	1.25
Methylprednisolone Acetate	1.25
Methylprednisolone Sodium Succinate	1.25
Methylprednisone	1.25
Methylprednisone Acetate	1.25
Prednisolone	1
Prednisolone Acetate	1
Prednisolone Hemisuccinate	1
Prednisolone Sodium Succinate	1

Standardized Medication Name	Scaling Factor
Prednisone	1
Prednisone Acetate	1
Triamcinolone	1.25
Triamcinolone Acetonide	1.25

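### SAP 1.1 omits the intravenous route from the primary event's steroid rule, very probably a drafting slip, and three per-protocol rules in SAP 6.2.13 differ from the protocol criteria they cite

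*SAP*

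**What the plan says.** **Primary event.** SAP 1.1 requires: "For all subjects, oral corticosteroid for at least 3 days or a single IM Corticosteroid (CS) dose is required". Protocol 1.1 requires: "i.v. or oral corticosteroid for at least 3 days or a single IM Corticosteroid (CS) dose is required". Protocol section 3 (Table 2) and section 7.2 give the same rule as the synopsis, again naming the intravenous route. In both documents, worsening that leads to hospitalisation or an emergency department (ED) visit also qualifies.

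Other parts of the SAP bear on how SAP 1.1 should be read. Section 4.1.3 describes the endpoint's events as "the same as protocol defined exacerbations". The first verification step in 6.2.10 is: "Clinical Review will be performed to evaluate each exacerbation to determine the event meets the protocol definition". Section 4.9 states that nothing departs from the analysis planned in protocol Amendment 4.

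**Per-protocol population.** SAP 6.2.13 lists reasons for exclusion, several of which refer to a numbered protocol criterion. For adults, the airflow rule is "pre-bronchodilator FEV1 <80% predicted (NHANES III" with a reference to Inclusion Criterion 3. That criterion, in protocol 5.1, uses "predicted normal values calculated by Quanjer reference equations".

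**The concern.** The rule that decides what counts as a primary event should read the same wherever it is stated. It matters more than usual here, because borrowing from MEA115588 is justified by both studies using the same exacerbation endpoint (protocol 4.4 and 9.1, SAP 2). A programmer or event reviewer working from SAP 1.1 alone would not count an intravenous course of 3 days or more in a subject who was neither admitted nor seen in an ED.

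The per-protocol rules raise a similar problem. Each one names a protocol criterion and then states something else, so those who determine the population under blind have two standards for the same subject.

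**Working it through.** **1. Primary event rule.** The three current protocol statements (1.1, 3, 7.2) name the intravenous route. The only SAP statement of the rule (1.1) does not. No change listed in the amendment log removes that route, so this is not a difference from superseded text.

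Slip or intended change? SAP 4.1.3, 6.2.10 and 4.9 all point to the protocol definition. SAP 4.4 plans a summary of "OCS plus other systemic routes of administration (oral, IV and IM) corticosteroids will be produced", and 6.2.14 says "Only corticosteroids administered via oral, IV and IM routes are to be considered" when the dose for an exacerbation is worked out. These last two are weaker evidence, since intravenous steroid can also be given during an admission that qualifies by itself. They do show that the SAP treats the intravenous route as ordinary exacerbation treatment. Taken together, a slip is much the likelier explanation.

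**2. Size if SAP 1.1 were nevertheless applied literally.** The share of events that qualify only through intravenous steroid is not given, so any size rests on an assumed share. The plan's own figures come first. With placebo rate 0.975, mepolizumab rate 0.585, dispersion 1.6 and 128 per arm:

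- SE = √[(1/0.975 + 1.6 + 1/0.585 + 1.6)/128] = √(5.935/128) = 0.2153.
- Power without borrowing = Φ(|ln 0.6|/0.2153 − 1.96) = Φ(2.372 − 1.960) = 66.0%. The plan says 66%.
- The SAP 4.2.1 mixture posterior reaches 95% at an observed ratio of 0.776, as in the plan. Probability of success = Φ[(ln 0.7762 − ln 0.6)/0.2153] = Φ(1.196) = 88.4%. The plan says 88.6%.

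Now remove an assumed share of events, equal in both arms, with dispersion unchanged and the threshold recalculated:

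| Assumed share lost | Power without borrowing | Success with borrowing |
|---|---|---|
| 0% | 66.0% | 88.4% |
| 5% | 65.0% | 88.0% |
| 10% | 63.8% | 87.6% |
| 20% | 61.3% | 86.7% |

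Unequal shares would also shift the ratio itself; the documents do not allow a figure for that.

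**3. Per-protocol rules.** SAP 6.2.13 lists 11 reasons. Seven cite a numbered criterion: Inclusion 3, 5, 6 and 7, Randomization 1 and 2, and Exclusion 14.

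| Cited criterion | Protocol | SAP 6.2.13 |
|---|---|---|
| Inclusion 3 (adults) | Quanjer 2012 reference, since Amendment 2 | NHANES III reference |
| Inclusion 5 | 9 documented months of inhaled steroid in 12, and the last 3 before Visit 1 mandatory | 9 documented months in 12; no mandatory last 3 |
| Randomization 2 | Hyperresponsiveness by methacholine or histamine | The same, plus a positive mannitol test |

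The rules citing Inclusion 6, Randomization 1 and Exclusion 14 match. The rule citing Inclusion 7 leaves out that the prior exacerbations needed systemic steroid, but that may be shorthand and is not counted.

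**4. Where the population is used.** The modified intent-to-treat population is primary (SAP 3 and 4.2.1). The per-protocol repeat of the primary analysis is firm in protocol 9.3.1 and optional in SAP 4.2.4. Per-protocol repeats are planned for the key secondary endpoints in SAP 4.3.2. All of these are supplementary or supportive.

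**The case against.** A reader might infer from SAP 1.1 that the primary endpoint has been narrowed. The documents do not support that: SAP 4.1.3, 4.9 and 6.2.10 tie events to the protocol definition. The percentages above for a literal reading therefore rest on assumed shares and on a reading that the SAP itself contradicts. They show only that even that reading would have a small effect.

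A reader might also infer that SAP 6.2.13 would keep ineligible subjects in the per-protocol population. That is too strong. The list is introduced as reasons that may apply, not as a closed set. The sentence governing it removes subjects whose protocol deviations could affect efficacy, and SAP 6.1.3 has deviations reviewed before unblinding. A subject without the mandatory 3 months of inhaled steroid, or with only a mannitol test, remains a protocol deviator and can be excluded on that ground. What stands is that such subjects could be kept if the specific rules were followed as written.

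The differences may also be intended. SAP 4.2.4 says the per-protocol repeat serves comparability with MEA115588, and NHANES III was this study's own reference before Amendment 2. The documents do not give the MEA115588 per-protocol rules, so this can be neither confirmed nor excluded. If it is the reason, the SAP should say so. The direction in which the FEV1 reference would move subjects cannot be shown either, because neither set of equations is in the documents.

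Finally, the SAP version history names protocol Version 01 as its basis, which might suggest a plan written on a superseded protocol. SAP 4.9 names Amendment 4, and the borrowing analysis entered with that amendment. The entry is clerical and changes no result.

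**Conclusion.** The wording differences are real and the point is minor. The missing intravenous route in SAP 1.1 is very probably a drafting slip. That is an inference, but a well-supported one, and as long as events are reviewed against the protocol definition the primary result is unlikely to change.

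Three of the seven per-protocol rules that cite a numbered criterion differ from it. They could misclassify membership, but the number of subjects affected is not given and only supportive analyses are exposed. Nothing here bears on the primary analysis population or on the success criterion.

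**What to change.** - In SAP 1.1, restore the intravenous route so that the rule matches protocol 1.1, 3 and 7.2.
- In SAP 6.2.13, align the FEV1 reference, the inhaled-steroid rule and the hyperresponsiveness rule with the current Inclusion Criteria 3 and 5 and Randomization Criterion 2. Alternatively, state explicitly that a difference is intended and why, for example comparability with MEA115588.
- Correct the protocol version in the SAP version history so that it agrees with SAP 4.9 (clerical only).

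The cost is SAP wording, with no new data or analysis. The 6.2.13 text should be settled before the blinded per-protocol determination, so that membership is not argued over after unblinding.
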